## STATISTICAL CONSIDERATIONS

**Feasibility and sample size determination.** Our primary objective is to determine feasibility of preoperative adjuvant stereotactic body radiotherapy for patients who are at high risk of local failure after prostatectomy. A confidence interval approach is used to estimate the sample size appropriate for this feasibility study (24, 25). We consider preoperative adjuvant stereotactic body radiotherapy feasible when the estimated treatment completion rate for an enrolled patient is at least 75%. For a two-sided 90% exact binomial confidence interval, a sample size of 12 patients yields a lower limit of the 90% confidence interval of at least 75% if the true proportion of patients completing treatment is 93%. A feasibility assessment of preoperative adjuvant stereotactic body radiotherapy is a required step prior to designing a larger trial.

**Estimation of eligible patients and enrollment.** Numbers of eligible patients are estimated based on projected patient populations. Eligible patients for the study are drawn from prostate cancer patients referred for treatment evaluation at UCLA Medical Center by the study investigators. This is anticipated to be 200 patients in 2016. At least 25% are anticipated to be eligible based on the risk classification of patients for our protocol (patients at high risk of recurrence). We estimate 75% of these patients will be surgical candidates. Standard treatments for these patients include either surgery (that includes adjuvant radiotherapy with or without androgen deprivation therapy) or definitive radiotherapy with concurrent androgen deprivation therapy. We estimate 40% of the patients will elect definitive radiotherapy with androgen deprivation. Of the remaining 60% of eligible patients, we anticipate that between 20 and 50% would be amenable to preoperative adjuvant radiotherapy. Our study is planned to accrue patients within three years. Therefore, there are sufficient numbers of patients eligible to participate in this study.

**Measurements of serological markers (secondary objective).** Circulating cytokines, PGE2, prostate-tumor specific antibodies, HMGB-1 protein and the tryptophan/kynurenine ratio in plasma will be quantified by ELISA. Tumor-specific CD4 and CD8 T cell activities to known HLA-matched, immunodominant, tumor-associated antigens will be assessed ex vivo by IFN $\gamma$ -ELISPOT and dextramer staining. The tumor antigens of choice will include PSA and PSMA. A repeated measures analysis of variance will be used to assess differences in these serological markers over time. In addition to the overall time effect in the ANOVA model, we plan to test specific contrasts

between serological markers pre-treatment (baseline) and the first measurement post SBRT (pre surgery), where we anticipate to observe an increase in circulating tumor-specific CD4 and CD8 T cell activity.

Multivariate profile analyses may be used when patterns for various markers emerge. These statistical analyses will be performed using IBM SPSS Statistics for Windows, Version 20.0. (Armonk, NY) statistical software.

**Measurements of intra-tumoral and intra-prostatic markers (secondary objective).** The immune response at the tumor site will be visualized through immunohistochemistry (IHC), with particular focus on T cells (CD3+), T regulatory cells (CD4+ CD25hi), tumor infiltrating myeloid-derived suppressor cells (CD11b+ Gr-1+ CD15+) and tumor-associated macrophages (CD11b+F4/80+). Levels of CSF1/CSF1R, tumor MHC I, PD-1 and PD-L1 are also of interest as are markers for EMT (vimentin, N-cadherin, E-cadherin), for neuroendocrine differentiation (chromogranin A, neuron specific enolase), AR protein and p53. IntMax (scale of 0-300) = (% of positive tumor cells [scale of 0-100]) X (intensity of staining based on 0-3 scale [scale of 0-3]) will be assessed for each marker. Comparisons in markers will be made between: 1- post SBRT prostatectomy specimens vs biopsy material pre-SBRT; and 2- post SBRT prostatectomy specimens vs archival tissue of prostatectomy specimens (that did not undergo RT).

For comparison between post SBRT prostatectomy specimens and biopsy material pre-SBRT, average IntMax will be compared using a paired t-test or Wilcoxon signed-rank test (if the IntMax scores do not follow a normal distribution). For comparison between post SBRT prostatectomy specimens and archived material, average IntMax will be compared using a t-test or Wilcoxon rank-sum test (if the IntMax scores do not follow a normal distribution).

**RNA and DNA exome sequencing (secondary objective).** Quality control will be performed on the raw sequence data from RNA-seq experiments, which contain multiple short-read sequences with Phred quality score information using FastQC and FASTX-Toolkit. Bowtie2 will be used to align reads, which will then be mapped to the reference genome by TopHat2. Raw reads from exome sequencing will be aligned via BWA and converted to BAM format, and processed with the Genome Analysis Toolkit software package. Comparisons will be made to existing sequencing data (TCGA) for localized prostate tumors matched for histology and Gleason grade. Functional annotation will be performed using Gene Ontology, KEGG, and Reactome.

**Stopping Rules for Toxicity.** Prior studies evaluating RT prior to prostatectomy demonstrate safety of pre-operative RT at doses of up to 54 Gy in 30 fractions (12). It is anticipated that toxicity in this study will be low because our dose is selected based on the prior studies.

Nevertheless, our trial will be stopped for toxicity if any treatment related toxicity of CTCAE v4.0 grade 3 or above is observed in more than two subjects during the study

period in the following categories: gastrointestinal, urinary, with the exception of temporary use of a catheter and urinary incontinence, which can occur after prostatectomy in the absence of radiotherapy.

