### **Study design:**

This is a single arm, Phase I feasibility study of SBRT followed by prostatectomy within 4 weeks for patients with prostate cancer at high risk of local failure after prostatectomy. A patient is considered to have completed treatment if they received the prescribed radiation and undergo prostatectomy within 4 weeks of completing radiotherapy.

NUMBER OF PATIENTS;

12 patients in 3 years with recruitment at UCLA Jonsson Comprehensive Cancer Center

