### **Objectives:**

**Primary Objective:** To assess feasibility of pre-operative SBRT in prostate cancer patients at high risk for recurrence after prostatectomy. We consider the trial feasible when the estimated treatment completion rate for an enrolled patient is 75%. A patient is considered to have completed treatment if they received the prescribed radiation and undergo prostatectomy within 4 weeks of completing radiotherapy.

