**OUTCOME MEASURES**

**Primary objective, feasibility:** A patient is considered to have completed treatment if they received the prescribed radiation dose of 24 Gy delivered in 3 fractions of 8 Gy within a span of 2 weeks and subsequently undergo prostatectomy within 4 weeks of completing radiotherapy.

**Secondary objective, safety and acute toxicity:** Patients will be evaluated during RT, prostatectomy, and at intervals of 3 months following completion of treatment for one year. At each visit, patients will complete the EPIC and IPSS questionnaires and will be assessed for CTCAE v4 toxicities.

**Secondary objective, correlative studies:** Assessments of the systemic immune response will utilize blood that is collected pretreatment, after completion of SBRT, and at 3 and 6 months post treatment completion. The local immune response (intratumoral) will utilize the resected prostatectomy specimen, pre-treatment biopsies, and archived tissue arrays of prostatectomy specimens that did not undergo RT. RNA- and exome-sequencing of irradiated prostate tumors will utilize the resected prostatectomy specimens, which will be compared to existing sequencing analyses of localized prostate cancers (TCGA) matched for histology and Gleason grade.

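### The sample size is justified by a 90% lower limit of at least 75%, but the verdict rests on the point estimate (9 of 12 is enough), so a feasible verdict carries less assurance than the sizing implies

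*Combined protocol and SAP*

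**What the plan says.** The trial is single-arm: "12 patients in 3 years with recruitment at UCLA Jonsson Comprehensive Cancer Center". The primary endpoint is completion of treatment, meaning that the patient receives the planned 24 Gy in 3 fractions within 2 weeks and must "subsequently undergo prostatectomy within 4 weeks of completing radiotherapy" (OUTCOME MEASURES).

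The verdict rule is in STATISTICAL CONSIDERATIONS, under feasibility and sample size determination. The approach is "feasible when the estimated treatment completion rate for an enrolled patient is at least 75" per cent. The Primary Objective, both in the opening synopsis and under Objectives, ties the verdict to the same estimated rate in slightly looser words: "We consider the trial feasible when the estimated treatment completion rate for an enrolled patient is 75" per cent.

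The sizing argument is in the same paragraph as the rule. It opens with "A confidence interval approach is used to estimate the sample size appropriate for this feasibility study". After the rule it names an exact binomial interval, two-sided at the 90% level, and gives as the reason for enrolling 12 that this number "yields a lower limit of the 90% confidence interval of at least 75% if the true proportion of patients completing treatment is 93" per cent.

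The document gives no minimum number of completers and no operating characteristics for the rule. It does not say how the interval bears on the conclusion.

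**The concern.** The same 75% bar is used twice in one paragraph: once for the estimated rate, which decides the verdict, and once for the lower confidence limit, which justifies the number of patients. Sizing a study so that a lower limit clears a threshold is normally done so that a positive result can be read as excluding values below that threshold. A reader will therefore tend to take a feasible verdict as evidence that the completion rate exceeds 75%. The stated rule gives no such evidence.

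This is the only primary endpoint, and the plan treats the assessment as a precondition for designing a larger trial. Whoever designs that trial needs to know how much a feasible verdict establishes. As written, the plan overstates it and does not disclose how often the rule passes when the true rate is below the bar.

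**Working it through.** **Inputs.** n = 12 (Study design). Verdict rule: estimated rate of at least 75%. Interval: two-sided 90% exact binomial, so 5% in the lower tail. Assumed true rate: 93%. The last three come from STATISTICAL CONSIDERATIONS. I assume that all 12 patients count in the denominator and that completions are independent with a common probability p.

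**Step 1. The plan's own figure.** The exact (Clopper-Pearson) lower limit for x completers is the 5% quantile of a Beta(x, 12 − x + 1) distribution, that is, the p at which P(X ≥ x) = 0.05. At 93% of 12, x = 0.93 × 12 = 11.16 and the lower limit is 67.9%. The stated figure of at least 75% does not reproduce. It appears only if 11.16 is rounded up to 12 of 12 (77.9%), or if the interval is a Wald interval, which is not exact: 0.93 − 1.645 × √(0.93 × 0.07 / 12) = 80.9%. That arithmetic is a separate matter. The point here would remain if it were corrected.

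**Step 2. The verdict rule as a count.** 0.75 × 12 = 9, so 9 or more completers is feasible and 8 of 12 (66.7%) is not.

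**Step 3. What the interval shows for each passing result.**

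| Completers | Estimate | Exact 90% lower limit | Verdict by the stated rule | Lower limit at least 75%? |
|---|---|---|---|---|
| 9 | 75.0% | 47.3% | feasible | no |
| 10 | 83.3% | 56.2% | feasible | no |
| 11 | 91.7% | 66.1% | feasible | no |
| 12 | 100% | 77.9% | feasible | yes |

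The last row can be checked by hand: p^12 = 0.05 gives p = 0.05^(1/12) = 0.779. Three of the four results that earn a feasible verdict miss the sizing standard. At 9 of 12 the full interval is 47.3% to 92.8%.

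**Step 4. How often the stated rule passes.** P(X ≥ 9) = Σ C(12, k) p^k (1 − p)^(12 − k), k = 9 to 12. At p = 0.60 the four terms are 0.14189 + 0.06385 + 0.01741 + 0.00218 = 0.2253. For comparison, P(X = 12) = p^12 is the pass probability if the lower limit itself had to reach 75%.

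| True rate | Stated rule (at least 9 of 12) | Lower-limit standard (12 of 12) |
|---|---|---|
| 50% | 7.3% | 0.02% |
| 60% | 22.5% | 0.2% |
| 65% | 34.7% | 0.6% |
| 70% | 49.3% | 1.4% |
| 75% | 64.9% | 3.2% |
| 93% | 99.2% | 41.9% |

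At the 75% bar the lower-limit standard passes 3.2% of trials, so meeting it would be evidence that the rate exceeds 75%. The stated rule passes 64.9% there.

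**The case against.** The strongest reply is that the plan has one verdict rule. The statistical section and both statements of the primary objective tie feasibility to the estimated rate. No sentence requires the lower limit to reach 75% for a verdict; the interval is introduced for estimating the sample size. That is correct, and it rules out three stronger readings.

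- A reader might infer that the plan holds two competing criteria, so that 9, 10 or 11 completers give opposite verdicts. Under the only stated rule, all three counts are feasible.
- A reader might note that 9, 10 or 11 completers occur in 57% of trials at a true 93% (99.2% − 41.9%) and take this as an error rate. It is not. The stated rule gives the right answer 99.2% of the time at that rate; the gap comes from promoting the sizing standard to a decision rule.
- A reader might see a further criterion in the objectives, where the rate simply equals 75%. Taken literally that would mean exactly 75%, which cannot be intended, and the statistical section settles it.

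It can also be said that a point-estimate rule is a legitimate choice for a 12-patient feasibility study, that the plan states no null rate, alpha or power, and that a rule of this kind is bound to pass about half the time near its threshold. All of this stands. So does the limit on the worst case: an interval reaching below one half arises, among passing results, only at 9 of 12.

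None of it answers the narrower point. If the limit plays no part in the verdict, the stated reason for 12 patients does not support the rule actually used. If it was meant to play a part, the rule is missing. The plan cites two references for the interval approach, but how they use the limit cannot be checked from the document.

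**Conclusion.** The point holds in this form: the plan justifies its sample size by a standard that its verdict rule does not deliver. The sizing sentence implies that a feasible verdict excludes completion rates below 75%. The rule requires only 9 of 12, where the exact 90% lower limit is 47.3%, and it passes 23%, 49% and 65% of trials at true rates of 60%, 70% and 75%.

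The rule is usable and need not change. The defect is in the justification given for it and in the strength that a reader would attach to the result. The percentages assume n = 12, all enrolled patients in the denominator and independent completions. If the number of patients were changed, the counts and percentages would change too, but a point-estimate rule would still not give the assurance of a lower-limit standard.

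**What to change.** In the synopsis, under Objectives and in STATISTICAL CONSIDERATIONS, state the rule once and identically as a count: feasible if at least 9 of 12 enrolled patients complete treatment.

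In STATISTICAL CONSIDERATIONS, replace the lower-limit justification with the operating characteristics of that rule: a feasible verdict in 23% of trials at a true 60%, 49% at 70%, 65% at 75% and 99% at 93%. Commit to reporting the exact 90% interval beside the verdict. Word the conclusion as an estimated completion rate of at least 75%, not as evidence that the rate exceeds 75%.

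If the sponsor intended the lower-limit standard, the rule at this sample size must read 12 of 12, and the plan should say that its chance of success is 42% at the assumed 93%.

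The sponsor should choose between the two before the completion data are examined. The cost is wording only, with no added patients, visits or data. A feasible verdict will be described as weaker than the present text suggests.

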**Protocol Overview**

SBRT	Prostatectomy	Tests at each Follow-up
24Gy in 3 fractions (8 Gy per fraction)	Open or robotic assisted prostatectomy within 4 weeks (preferable 2 weeks) of SBRT	CTCAE toxicity scores, QOL-EPIC & IPSS scores, blood (including PSA)

[figure not shown]
Study Design: Prospective Phase I  
 Sample size: 12 patients, single-institutional  
 Outcome: Feasibility assessment (percent of patients completing scheduled treatment)  
 Treatment: SBRT, prostatectomy  
 RT targets: Prostate PTV = prostate and SV (only if involved on MRI or biopsy)

Target Prescription Doses:

Prostate PTV 24 Gy in 3 fractions, 8 Gy per fraction

RT Technique: image-guided SBRT via robotic radiosurgery, IMRT, or VMAT, with daily and intra-fraction Image-guidance (MRI-based, fiducial-based or CBCT-based)

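### The sample-size statement is wrong: with 12 patients the exact 90% lower limit reaches 75% only if all 12 complete, which has a 42% chance at the assumed true rate of 93%

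*Combined protocol and SAP*

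**What the plan says.** The sample size is 12, single arm: "Sample size: 12 patients, single-institutional" (Protocol Overview; the number is repeated under Study design). The statistical case for it is one sentence in Statistical Considerations, under feasibility and sample size determination. It names the method, "For a two-sided 90% exact binomial confidence interval, a sample size of 12 patients", and gives the result: "a sample size of 12 patients yields a lower limit of the 90% confidence interval of at least 75" per cent, "if the true proportion of patients completing treatment is 93" per cent. It does not say how many patients must complete, or how likely the stated limit is.

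The same paragraph calls the treatment "feasible when the estimated treatment completion rate for an enrolled patient is at least 75" per cent. It does not say whether the estimate means the observed proportion or the lower confidence limit, and neither statement of the primary objective settles this. Completion is a yes/no outcome for each patient: all the radiation within two weeks, and then the patient must "subsequently undergo prostatectomy within 4 weeks of completing radiotherapy" (Outcome Measures). The rate is the "estimated treatment completion rate for an enrolled patient", and no allowance for dropout is given.

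**The concern.** With 12 patients the completion rate moves in steps of 8.3 percentage points (1/12), and an exact 90% interval around any such rate is wide. A lower limit only 18 points below an assumed 93% looks too tight for this method. The result also cannot follow automatically from a true rate. The limit depends on how many patients actually complete, so the plan can only promise it with some probability.

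The sentence is the only quantitative support for the sample size of the primary objective, and the plan treats the feasibility result as a prerequisite for a larger study. If the sentence is wrong, readers will expect precision that the design does not deliver. One late operation or one withdrawal would be enough to expose the gap.

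**Working it through.** **Inputs** (all from Statistical Considerations): n = 12; two-sided 90% exact binomial interval, so 5% in each tail; target lower limit 75%; assumed true completion rate 93%.

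**Formula.** The exact (Clopper-Pearson) lower limit for x completers out of n is the 5% point of a Beta(x, n − x + 1) distribution. When all n complete it reduces to 0.05^(1/n).

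**Results for n = 12**

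| Completers | Observed rate | Exact lower limit | Probability if true rate is 93% |
|---|---|---|---|
| 12 | 100% | 0.05^(1/12) = 77.9% | 0.93^12 = 41.9% |
| 11 | 91.7% | 66.1% | 12 × 0.07 × 0.93^11 = 37.8% |
| 10 | 83.3% | 56.2% | 15.7% |
| 9 | 75.0% | 47.3% | 3.9% |
| 8 or fewer | 66.7% or less | 39.1% or less | 0.8% |

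Only 12 out of 12 reaches 75%. The chance of missing it at a true rate of 93% is 1 − 0.419 = 58.1%.

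**Attempts to reproduce the plan's figure**

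- *93% read as the observed rate.* 0.93 × 12 = 11.16 completers, which cannot occur. Putting the fraction into the exact formula gives 67.9%.
- *Nearest attainable result.* 11/12 gives 66.1%.
- *Average lower limit at a true rate of 93%.* 0.419 × 77.9% + 0.378 × 66.1% + 0.157 × 56.2% + 0.039 × 47.3% + a small remainder = 68.6%.
- *One-sided 90% exact limit.* 71.3% at 11/12; 72.9% at 11.16/12.
- *Other intervals at 11/12.* Agresti-Coull 68.3%, Wilson 69.9%, mid-p 70.1%, Jeffreys 71.7%.
- *Wald (normal) approximation at 93%.* 0.93 − 1.645 × √(0.93 × 0.07 / 12) = 0.93 − 0.121 = 80.9%, or 80.9% − 1/24 = 76.7% with a continuity correction. Of the methods tried, only this one exceeds 75%, and the plan specifies an exact interval.

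**Shortfall.** 75 − 66.1 = 8.9 points at 11/12; 75 − 67.9 = 7.1 points at the fractional count; 75 − 68.6 = 6.4 points on average.

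**Sensitivity to the true rate.** At 90% the chance of 12/12 is 0.90^12 = 28%. An even chance needs a true rate of 0.5^(1/12) = 94.4%, and an 80% chance needs 0.8^(1/12) = 98.2%.

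**For scale.** At a true rate of 93%, the smallest trial with at least an 80% chance of an exact lower limit of 75% or more has 29 patients. It needs 26 completers (lower limit 75.4%), with probability 85.8%.

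**The case against.** Four points can be made for the plan.

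1. **The sentence attaches no probability to its claim, and one reading makes it come out.** At a true rate of 93% the single most likely count is 12/12 (41.9% against 37.8% for 11/12), and 12/12 gives 77.9%. This is true, but the plan does not state that reading. The median count is 11, and the limit is still missed more often than it is met.

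2. **Feasibility may be judged on the point estimate.** The wording allows this. On that rule 9 of 12 is enough, which has a 99.2% chance at a true rate of 93%. This stands as a limit on the consequence: the 42% is the chance of the claimed precision and should not be read as the chance of a feasible verdict. It does not rescue the sentence, which is wrong under either rule. On the point-estimate rule a true rate of exactly 75% would still be called feasible 64.9% of the time, and 9/12 carries a lower limit of 47.3%. The interval statement is the plan's only stated assurance on precision.

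3. **This is a small single-centre pilot.** Agreed. That argues for describing 12 honestly as a pilot size, and no increase is asked for.

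4. **The section cites two sources for the confidence-interval approach that are not in the supplied reference list.** They cannot be checked here, but the named exact method, n and level fix the limits without them.

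**Conclusion.** The statement is wrong as written. With 12 patients and a two-sided 90% exact binomial interval, the lower limit reaches 75% only if every patient completes. At the plan's assumed true rate of 93% that has probability 41.9%, so the claimed property fails in 58% of such trials. The lower limit to expect is about 66% to 69%, an overstatement of 6 to 9 percentage points. The calculation takes patients as independent with a common completion probability and all 12 enrolled patients in the denominator, as the plan's own binomial method and definition imply. It does not assume that the lower limit is the decision rule. The error lies in the justification of the sample size. Whether it also makes a feasible verdict unlikely depends on a rule the plan leaves open.

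**What to change.** Keep 12 patients and replace the sentence with the correct figures, for example:

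> With 12 patients the exact two-sided 90% lower limit is 77.9% if all 12 complete, 66.1% if 11 complete and 56.2% if 10 complete. If the true completion rate is 93%, the probability that the lower limit is at least 75% is 42%.

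Present 12 as a pilot size with this precision, not as a number derived from the 75% target. In the same paragraph, say whether the 75% criterion applies to the observed proportion or to the lower limit, and give the number of completers it requires: 9 of 12 in the first case, 12 of 12 in the second.

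The cost is one paragraph of wording. No patients are added and no endpoint or procedure changes. The stated precision becomes less favourable. If the sponsor wants the 75% lower limit as a real design property at a true rate of 93%, the trial would need about 29 patients, but the correction does not require that.

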#### **• Secondary Objectives:**

- To assess safety and acute toxicity of SBRT followed by prostatectomy. This will be based on CTCAE version 4.0 and patient reported quality of life (EPIC and IPSS questionnaires).
- Investigation of the radiobiology of SBRT in prostate cancer using resected prostate tumor tissue. For the correlative genomic analyses, prostate lesions at the time of prostatectomy will be processed for RNA and exome sequencing and compared to existing sequencing data for localized prostate cancers. We will utilize both supervised and unsupervised analyses of

- Pathway activation from RNA-seq data sets in order to determine which pathways are enriched after irradiation.
- Evaluation of the nature of the immune response to prostate cancer generated by SBRT.
    - Systemic immune response. Blood that is collected pre SBRT, between 0 and 4 weeks after SBRT, and at 3 and 6 month intervals after SBRT will be assessed as follows: PBMCs will be isolated over Ficoll-gradients and stored frozen until analysis. Lymphoid and myeloid subset phenotyping will be assessed by antibody staining and multi-color flow cytometry (LSR-Fortessa, BD). Circulating cytokines, PGE2, prostate-tumor specific antibodies, HMGB-1 protein and the tryptophan/kynurenine ratio in plasma will be quantified by ELISA. Tumor-specific CD4 and CD8 T cell activities to known HLA-matched, immunodominant, tumor-associated antigens will be assessed ex vivo by IFN  $\gamma$  -ELISPOT and dextramer staining. The tumor antigens of choice will include PSA and PSMA.
    - Local immune response. The immune response at the tumor site will be visualized through immunohistochemistry (IHC), with particular focus on T cells (CD3+), T regulatory cells (CD4+ CD25hi), tumor infiltrating myeloid-derived suppressor cells (CD11b+ Gr-1+ CD15+) and tumor-associated macrophages (CD11b+F4/80+). Levels of CSF1/CSF1R, tumor MHC I, PD-1 and PD-L1 are also of interest as are markers for EMT (vimentin, N-cadherin, E-cadherin), for neuroendocrine differentiation (chromogranin A, neuron specific enolase), AR protein and p53. Comparisons will be made to pre-treatment biopsy material when possible and to tissue microarrays of non-irradiated prostatectomy specimens.

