#### **Prostatectomy:**

Radical prostatectomy will be performed, either open or robot assisted, within 4 weeks after SBRT (preferably 2 weeks). After resection, the prostate is sectioned from base to apex into 5-7 slices depending on the size of the prostate. Slices 2 and 4 are kept fresh on ice, while all other slices are fixed in formalin and embedded in paraffin. A slide is cut and stained from the paraffin sections for pathologic diagnosis and the remaining tissue will be kept indefinitely in pathology and can be used for research.

Frozen section is prepared from the fresh tissue (slices 2 and 4) for rapid diagnosis. Part

of the fresh tissue is used for research and the remaining fresh tissue is frozen indefinitely and can be used for research.

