**Follow-up:**

- 0 to 4 weeks after the final fraction of radiation, patients will have approximately 60 mLs of blood drawn for serum translational biomarker research. Patients will also be evaluated by their physician and Adverse Events and Concomitant Medications will be assessed. EPIC and IPSS questionnaires will also be administered at this time.
- Patients are followed every three months ( $\pm$  4 weeks) for one year post surgery. At each follow-up visit, patients are evaluated for CTCAE (version 4.0) toxicity scores, and the EPIC and IPSS questionnaires will be administered. Blood draws (~5 mLs) to assess PSA are drawn at each of the follow-up visits unless PSA lab evaluations have already been done within 4 weeks of the study visit. In addition, at the 3 month and 6 month follow-up visits, approximately 60 mLs of blood will be drawn for serum translational biomarker study. After one year of follow-up, patients will be seen as per routine care.

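### The overall time effect and the 3- and 6-month blood markers reflect SBRT plus prostatectomy, and the plan does not say which result answers the SBRT immune objective

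*Combined protocol and SAP*

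**What the plan says.** All references are to the combined protocol and SAP.

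- **Objective.** Under Secondary Objectives: "Evaluation of the nature of the immune response to prostate cancer generated by SBRT". The systemic part of that objective uses "Blood that is collected pre SBRT, between 0 and 4 weeks after SBRT, and at 3 and 6 month intervals after SBRT".
- **Timing of surgery.** The Prostatectomy section puts the operation no later than 4 weeks after SBRT, with 2 weeks preferred.
- **Late draws.** The Follow-up section says that "at the 3 month and 6 month follow-up visits, approximately 60 mLs of blood will be drawn for serum translational biomarker study", and those visits run "for one year post surgery". OUTCOME MEASURES places the same draws "at 3 and 6 months post treatment completion".
- **Second draw.** Follow-up says: "0 to 4 weeks after the final fraction of radiation, patients will have approximately 60 mLs of blood drawn". Radiation Planning and the Table of Study Assessments give the same 0-4 week window.
- **Analysis.** Under Measurements of serological markers: "A repeated measures analysis of variance will be used to assess differences in these serological markers over time". That section then adds, beyond the overall time effect, contrasts of baseline with the first post-SBRT measurement, which it describes as taken before surgery. An expected rise in tumor-specific CD4 and CD8 T-cell activity is attached to this contrast.
- **Comparators.** The trial has one arm. Non-irradiated comparators are archived tissue and existing sequencing data. None is a blood sample.

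**The concern.** The objective is about SBRT, but two of the three post-baseline draws come after the prostate has been removed. A test of change across all four draws cannot tell an SBRT effect from an effect of the operation. With a single arm and no surgery-only blood control, neither a larger sample nor a different repeated-measures model would separate them.

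The plan does not say whether the overall time effect or the pre-surgery contrast answers the objective, and it sets no limit on how the time effect or the late values may be interpreted. A change caused by surgery could therefore be read as SBRT-induced immunity. That matters because Clinical - Translational Relevance says that understanding these changes could inform the use of immunomodulatory treatment.

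**Working it through.** **No planned figure to reproduce.** The plan gives no effect size, SD, correlation, alpha or power for the serological analysis. The sample of 12 was set for feasibility. The argument rests on the order of events.

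**Step 1: order of draws and surgery.**

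| Draw | Time | Relative to prostatectomy, if treated as planned |
|---|---|---|
| 1 | before SBRT | before |
| 2 | 0-4 weeks after SBRT | meant to be before; the window does not ensure it |
| 3 | 3-month visit | after |
| 4 | 6-month visit | after |

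The sections anchor draws 3 and 4 differently (SBRT, treatment completion, surgery), but the order is the same under each. The least favorable case counts 3 months from SBRT and uses the full 4-week visit window: about 13 − 4 = 9 weeks after SBRT. Surgery is at most 4 weeks after SBRT, so draw 3 is still at least about 9 − 4 = 5 weeks after surgery.

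**Step 2: what each test addresses.** Four draws give 4 − 1 = 3 degrees of freedom for time. Only the contrast of draw 2 with draw 1 avoids surgery, provided draw 2 precedes it. Contrasts involving draw 3 or 4 carry the SBRT and surgical effects together.

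**Step 3: illustration.** The following are assumptions, not figures from the documents: two-sided alpha 0.05, within-patient correlation ρ of 0.3 to 0.7, zero SBRT effect, and a shift of δ SD at draws 3 and 4 only. With time means (0, 0, δ, δ), each deviates from the overall mean by δ/2. The squared deviations sum to 4 × (δ/2)² = δ², so the noncentrality of the overall F test is

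λ = n δ² / (1 − ρ), with 3 and (4 − 1)(12 − 1) = 33 degrees of freedom.

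For n = 12, δ = 0.8 and ρ = 0.5, λ = 12 × 0.64 / 0.5 = 15.36. Simulation (20,000 runs per setting) gives these rejection rates, and the noncentral F distribution agrees closely:

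| Shift after surgery | ρ = 0.3 | ρ = 0.5 | ρ = 0.7 |
|---|---|---|---|
| 0.5 SD | 34% | 47% | 70% |
| 0.8 SD | 75% | 88% | 99% |
| 1.0 SD | 92% | 98% | 99.9% |

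In the same runs the paired test of draw 2 against draw 1 rejected in about 5%.

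**Step 4: if some second draws follow surgery.** With a 1.0 SD shift, ρ = 0.5 and no SBRT effect, the paired test rejects in about 9% of trials when 25% of second draws fall after surgery, and in about 27% when 50% do. The contrast is protected only if the order is secured.

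**The case against.** The strongest reply is that the plan already contains the right analysis. It specifies the baseline versus pre-surgery contrast and attaches its only directional serological hypothesis to it. This stands: a reader might infer that the plan has no SBRT-specific blood test, and that would be wrong. What remains is that the contrast sits beside the time effect without priority, while the objective still lists the late draws as evidence on SBRT.

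Several stronger readings are also tempting, and the documents do not support them:

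- **That a significant time effect would be reported as SBRT-induced.** The plan says only that differences over time will be assessed. Misattribution is a risk, not a stated intention.
- **That the post-surgical draws would hide a brief early rise.** The contrast does not depend on a significant overall test, so it can still detect such a rise.
- **That the pre-surgery contrast isolates SBRT.** It is an uncontrolled before-after change. Patients on ADT are allowed, and no adjustment is stated.
- **That the time course should be dropped, or that only one test is acceptable.** That is a preference. The time course legitimately describes the combined regimen. A second draw taken right after the last fraction could also miss a response that develops later.

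The stakes are also limited. This is a secondary correlative objective in a 12-patient study, and it touches neither the feasibility endpoint nor the toxicity stopping rule.

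**Conclusion.** The concern holds as a problem of attribution. In patients treated as planned, the overall time effect and any 3- or 6-month change are joint effects of SBRT and prostatectomy, and the design cannot separate them. This follows from the order of events and the absence of a non-irradiated blood control, and needs no numerical assumption. The rejection rates of 34% to 99.9% depend on assumed shifts and correlations, so they illustrate the mechanism and do not estimate its size in this trial. The analysis closest to the objective is already planned, but it lacks priority and its second draw is not secured before surgery. The weight is moderate: the correction is worth making because it changes what the trial may validly conclude about SBRT.

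**What to change.** 1. In Secondary Objectives and in Measurements of serological markers, name the planned pre-SBRT to pre-surgery contrast as the main analysis of the systemic immune objective for each marker. Describe it as an uncontrolled before-after change.
2. Keep the repeated-measures time course, but label it and the 3- and 6-month values as effects of the combined SBRT plus prostatectomy regimen.
3. Show later draws as change from the pre-surgery draw as well as from baseline, so that the step across surgery is visible.
4. Reconcile the second-draw window in Radiation Planning, Follow-up and the Table of Study Assessments, which overlaps the surgical window, with the pre-surgery description in the analysis section. Record the order of draw and operation, and analyze as pre-surgery only those second draws actually taken before it.

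The cost is wording, with no added patients, draws or assays. The trial gives up attributing later immune changes to SBRT alone, and any second draw taken after surgery is lost to the main contrast.
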